## 2.2 Trial rationale

The safety and tolerability of AE0117 has been demonstrated in the clinical studies conducted to date. This trial will provide data on the effect of food on the oral bioavailability of AEF0117 to support the next stage of the clinical development of the drug.

## 2.3 Risk-benefit assessment

### 2.3.1 Known and expected potential risks

This protocol represents an early trial of AEF0117 that will be conducted in parallel with an ongoing phase 2b trial; therefore, the long-term risks and benefits in humans are unknown. Safety data from preclinical studies with AEF0117 do not give rise to safety concerns, details can be found in the investigator's brochure [9].

In phase 1 single and multiple ascending dose studies in healthy volunteers, doses in the range of 0.2 to 6 mg were investigated. In total, 18 volunteers received doses of 0.6, 2, or 6 mg once daily for 7 days, and 30 volunteers received single doses of 0.2, 0.6, 2, or 6 mg. There were no SAEs reported in the 2 studies. AEF0117 was considered safe and with a limited number of mild TEAEs (except 2 TEAEs which were moderate) not related to the dose of AEF0117. There were only 2 noticeable TEAEs in 2 different participants. One participant in AEF0117-101 who received the single administration of 2 mg of AEF0117 showed an increase in creatine phosphate kinase (CPK) and myoglobin. One participant in AEF0117-102 developed a skin rash 30 minutes after the first administration of 0.6 mg of AEF0117 and was withdrawn from the trial.

In study AEF0117-201, 26 cannabis users, 0.06 and 1.0 mg AEF0117 was given once daily for 5 days and was also well tolerated.

Because this drug is investigational, all its side effects are not known. There may be rare and unknown side effects. Some of these may be life-threatening.

AEs across the 3 clinical studies performed with AEF0117 seen in 2 or more participants were headache, dizziness, gastrointestinal symptoms (dyspepsia and nausea), thermal burn, and abnormal/increased CPK.

With almost any drug, there is the possibility of having an allergic reaction. Symptoms of an allergic reaction include:

- Swelling, especially of the face and throat
- Difficulty breathing
- Itchy skin, rash, and hives
- Watery eyes
- Runny nose

## Pregnancy

This is an experimental compound with unknown risks during conception and pregnancy in humans. Both male and female participants will be asked about adequate method of contraception they are using. We will also discuss with male participants to ensure that whatever adequate method of contraception males are using, their female partners are also using an adequate method of contraception.

## Inpatient research designs

There are minor risks of isolation, boredom, and inactivity associated with living in the research facility. In participants tested at the site to date under similar conditions, such problems have been minimal.

## Blood drawing

During the screening assessments, venous blood sample will be collected for medical evaluation, and blood samples will be collected for PK assessments. Blood drawing may cause lightheadedness, fainting, bleeding, pain, redness, bruising, blood clots, which may cause inflammation, swelling, irritation or infection at the site of the IV tube or needle site. There may also be some discomfort during the insertion of the IV tube into the arm.

## COVID-19

Participants will be asked to exercise caution when traveling in public and follow public health guidelines, such as wearing masks in public and avoiding crowds and to stay informed about public health recommendations and guidelines regarding COVID-19, such as those issued by the Centers for Disease Control (CDC.gov) and local government guidelines and directives.

### 2.3.2 Known and expected potential benefits

The participants in this trial are not expected to get any immediate benefit of their participation. However, they will contribute to the process of developing a potential new therapy in an area of high unmet need.

### 2.3.3 Safety management plan / mitigation of risks

In this trial, participants will be closely monitored through AE monitoring, clinical safety laboratory tests, vital signs, 12-lead ECGs, and physical examination assessments according to the schedule of procedures detailed in section 1.3.

After dosing, participants will be monitored closely for AEs until discharge from the clinic, and regular vital signs measurement and ECG recording will be performed. On Day 2 before discharge, safety laboratory tests, brief physical examination, vital signs, and ECG will be performed.

Suicidality will be assessed by use of the C-SSRS before dosing and at discharge.

In emergency situations, the investigator should contact the sponsor's medical monitor, indicated below:

Trial Medical Monitor  
[name], PhD  
Aelis Farma  
[contact]  
Email: [[contact]](mailto:[contact])

#### **2.3.4 Overall risk-benefit conclusion**

Considering the measures taken to minimize risk to participants participating in this trial, the limited potential risks in association with AEF0117 dosing and the trial design are justified by the anticipated benefits of a potential new therapy to treat CUD.

### 3 TRIAL OBJECTIVES AND ENDPOINTS

Objectives	Endpoints
Primary objective	Primary endpoints
To determine the bioavailability of orally administered AEF0117 after fed conditions relative to fasting conditions in healthy volunteers.	Bioavailability of AEF0117 after fed conditions relative to fasting conditions. PK parameters $C_{max}$ , $T_{max}$ , $T_{lag}$ , $AUC_{0-t}$ , $AUC_{0-\infty}$ determined based on plasma concentration in serial blood sample collections up to 312 hours after dosing.
Secondary objectives	Secondary endpoints
To evaluate other PK parameters of AEF0117 in healthy volunteers.	PK parameters $\%AUC_{extrap}$ , $C_{min,24h}$ , $t_{1/2}$ , CL/F, and Vd/F determined based on plasma concentration in serial blood sample collections up to 312 hours after dosing.
To evaluate safety and tolerability of a single dose of 1 mg AEF0117 in healthy volunteers.	Vital signs (BP, HR) and ECG. AEs.
Exploratory objective	Exploratory endpoints
To characterize potential metabolites regarding plasma PK.	Identification of metabolites, to the extent feasible, and PK of potential metabolites of AEF0117 in plasma. To the extent concentration in plasma allows, the following PK parameters will be estimated: $C_{max}$ , $T_{max}$ , $AUC_{0-t}$ , $AUC_{0-\infty}$ , and $C_{min,24h}$ , and $C_{last}$ .

 Exploratory endpoints will be reported separately.

### 4 TRIAL DESIGN

#### 4.1 Overview

This is a single center, randomized, parallel-group, 2-arm, open-label, single-dose trial in healthy male and female volunteers aged 18–55 years to obtain data on the effect of food on the oral bioavailability of AEF0117.

A total of 32 healthy volunteers are planned to be enrolled. Participants will be randomized in a 1:1 ratio to receive 1 dose of AEF0117 1 mg in fasted condition (16 participants) or fed condition (16 participants). The participants will be divided into smaller cohorts of minimum 2 participants for operational reasons (adjusted to capacity of the research facility) and each cohort will include 1 fasting participant and 1 participant receiving breakfast prior to dosing.

The total trial duration for an individual participant will be up to 6 weeks (42 days) from screening (up to 28 days prior to dosing) to the final follow-up visit (14 days after dosing).

After screening, the trial includes 2 days where the participants are confined at the research facility, and thereafter 7 visits to the site (6 visits and a follow-up visit). Participants will stay in the research facility from the afternoon prior to dosing on Day 1 and until after collection of the blood sample 24 hours after dosing (i.e., Day 2) and then be discharged.

Participants will be admitted to the research facility during the afternoon on Day -1 where it will be verified that the participants are still eligible according to the inclusion and exclusion criteria,

and the baseline assessments will be performed. After an overnight stay in the research facility, participants will be randomized to fasted or fed state and dosed with a single oral dose of 1 mg AEF0117.

Blood samples for determination of AEF0117 and potential metabolites of AEF0117 in plasma will be collected before dosing and repeatedly for up to 2 weeks after dosing.

Safety will be monitored throughout the trial by assessment of AEs, suicidal risk, clinical safety laboratory parameters, pregnancy tests (females only), vital signs, ECGs, and physical examinations.

The schedule of activities summarizing all procedures is provided in section 1.3, and a description of procedures by visit is provided in section 8.1.

## 4.2 Scientific rationale for the trial design

### 4.2.1 Justification for design and parameters

This trial will examine the effects of food on AEF0117 bioavailability in healthy volunteers. Standard PK parameters will be calculated, and a high fat meal will be served according to current guidance [10].

A parallel-group design has been chosen since detectable plasma concentration has been observed 2 weeks after discontinuation of multiple dosing of 1 mg/day due to the long elimination half-life of AEF0117 in humans. A crossover design would have required a long washout period with a potential risk of a high dropout rate.

As AEF0117 is a lipophilic compound it is anticipated that intake of a high fat meal will introduce a slight food effect i.e., increase the bioavailability, and the trial has been powered for such an effect. A total of 32 participants will be randomized 1:1 to fed or fasted conditions with an aim to complete 14 in each group. In alignment with FDA guidance [10, 11], at least 12 participants will complete the 72-hour PK sample in each group.

### 4.2.2 Justification for dose and route

AEF0117 is formulated as a soft capsule for oral administration. In this parallel-group food-effect bioavailability trial, a single dose will be administered to each participant.

The 1 mg dose has been selected since it is considered the highest therapeutic dose and has been shown to reduce the abuse-related subjective effects of cannabis and its self-administration in a phase 2a trial. Once daily administration of 1 mg dose for 5 days in patients with CUD has shown good safety and tolerability. In healthy volunteers, multiple dosing of up to 6 mg once daily for 7 days was considered safe and well tolerated with no SAEs, and only 2 moderate and no severe TEAEs.

## 4.3 End of trial definition

The end of the trial is defined as the last follow-up visit for the last participant.

## 5 TRIAL POPULATION

### 5.1 Rationale for the trial population

Healthy male and female volunteers will be enrolled in this trial in accordance with current guidance for food-effect bioavailability studies [10]. The aim is that at least 30% of the participants will be female.

### 5.2 Planned sample size and number of trial sites

This will be a single center trial conducted in US.

A total of 32 participants are planned to be randomized to fed or fasted condition.

### 5.3 Participant selection criteria

#### 5.3.1 Inclusion criteria

To be eligible for participation in this trial, the individual participant must meet all the following criteria at screening and/or on admission at Day -1:

1. Healthy, non-smoking male or female of any race, 18 to 55 years old, both inclusive.
2. Both males and female participants must use highly effective contraception during the entire trial period. Male participants should refrain from donating sperm or planning a pregnancy throughout the trial. Heterosexually active male participants must agree to use double-barrier contraceptive methods: male condoms and spermicide. Heterosexually active females are only eligible if they are documented to be surgically sterile (e.g., hysterectomy, tubal ligation) or post-menopausal (amenorrhea >1 year and FSH >25.8 mIU/mL) and with a negative pregnancy test.
3. A BMI of 22.0 to <35.0 kg/m^2.
4. Be informed of the nature of the trial and provide signed informed consent to participate in the trial prior to any trial-specific procedures.
5. After being shown the high fat meal, understands and accepts that the entire meal should be consumed within 30 minutes.
6. Be legally competent and able to communicate effectively (in English) with trial personnel.

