#### 5.3.2 Exclusion criteria

To be eligible for participation in this trial, participants must not meet any of the following criteria at screening and/or on admission at Day -1:

1. Tobacco cigarette smokers within the last 3 months prior to dosing with trial drug.
2. Any disease or condition that might compromise the cardiovascular, hematologic, renal, hepatic, pulmonary (including chronic asthma), endocrine (e.g., diabetes), central nervous, or

gastrointestinal (including an ulcer and cholecystectomy) systems, or any clinical laboratory values assessed as potentially clinically significant by the investigator.

3. Blood pressure outside normal range (140/80 mmHg systolic/diastolic) and considered potentially clinically significant.
4. Congenital long QT syndrome.
5. A corrected QT interval (Fridericia's – QTcF) >450 msec (male) or >470 msec (female).
6. A history of alcoholism or drug addiction within the past 2 years, recent use (in the last month) of any illicit drugs, or positive results from a urine screen for substances of abuse or from an alcohol breath test.
7. A history of or current serious mental illness including active or recent suicidal ideation, severe psychological distress (e.g., active suicidal plans, psychosis, debilitating panic disorder) and/or an abnormal C-SSRS result.
8. Severe learning disability, brain damage, or pervasive developmental disorder.
9. A history of difficulty donating blood or inadequate venous access.
10. Clinically significant anemia or low hemoglobin levels (<11.5 g/dL for women and <13 g/dL for men) at screening, donation of >250 mL of blood or plasma or received any blood or plasma for medical/surgical reasons within the 30 days prior to receiving trial drug, or intention to donate blood or plasma within 1 month after receiving trial drug.
11. History of or current HIV or hepatitis B or C.
12. History of COVID-19 within 4 weeks prior to Day -1, or positive COVID-19 test, according to standard procedures at the site, at screening or Day -1.
13. Positive serum pregnancy test ( $\beta$ -hCG) at screening or positive urine pregnancy test at Day -1 confirmed by a serum pregnancy test result.
14. Allergies to the trial drug and known allergies to pregnenolone or to corn and corn derivatives.

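### Male contraception and the bar on sperm donation are tied to trial time, not to the dose: they end 12 to 14 days after dosing for a completer and at no clear date for a man who leaves early (minor, safety only)

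*Protocol*

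**What the plan says.** Criterion 2 appears in the same form in the synopsis (1.1) and in 5.3.1. It asks both sexes to use highly effective contraception for the whole trial period, asks heterosexually active men to use condom plus spermicide, and states: "Male participants should refrain from donating sperm or planning a pregnancy throughout the trial". Section 4.1 gives the length of an individual's trial: "The total trial duration for an individual participant will be up to 6 weeks (42 days) from screening" to the final follow-up visit. Section 8.1.6 and the schedule in 1.3 place that visit at Day 14 ±1, 312 ± 24 h after dosing.

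On risk, the Pregnancy paragraph of 2.3.1 says "This is an experimental compound with unknown risks during conception and pregnancy in humans". It adds that the site will discuss contraception with men so that "their female partners are also using an adequate method of contraception". On persistence, 4.2.1 reports that "detectable plasma concentration has been observed 2 weeks after discontinuation of multiple dosing of 1 mg/day due to the long elimination half-life".

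Section 7.3.10 limits female participation to women of non-childbearing potential. It requires a pregnancy in a participant or partner that occurs during the trial to be reported within 24 hours, and it states that pregnancy is not an SAE. Neither criterion 2, 2.3.1 nor 7.3.10 gives a period counted from the dose.

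**The concern.** What matters for a partner's exposure is time since the dose, and criterion 2 does not use it. Its end point depends on when the man's participation ends. That is a defined visit for a completer but is unclear for someone who is dosed and then leaves.

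The point concerns men, because female participants must be of non-childbearing potential. If the aim of at least 30% women (5.1) is just met, that is 10 women (0.30 × 32 = 9.6, rounded up) and 22 men. After the last visit, or after an earlier exit, these men have no stated period to observe.

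Reporting has a related gap. A pregnancy conceived in the two weeks after dosing may well be recognized only after the last visit. Section 7.3.10 does not say how such a pregnancy reaches the sponsor. Section 7.3.2 does not oblige the investigator to seek adverse events actively once participation has ended, and its provision for late events covers related SAEs in participants, whereas pregnancy is not classed as an SAE.

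At stake are the safety of partners and the completeness of pregnancy reporting. Sample size, power and the fed/fasted comparison are untouched.

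**Working it through.** **1. When the precautions end for a completer.** Inputs: last visit at 312 ± 24 h (1.3), Day 14 ±1 (8.1.6), dosing on Day 1.
- Earliest: 312 − 24 = 288 h; 288 / 24 = 12 days.
- Nominal: 312 / 24 = 13 days.
- Latest: 312 + 24 = 336 h; 336 / 24 = 14 days.

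The plan's own duration reproduces: 28 days before dosing + 14 days after = 42 days (4.1). The 14 days used there is the upper end of the visit window.

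**2. When they end for a dosed man who leaves early.** Three statements bear on this.
- Section 5.4.1 places the early termination assessments at the time of discontinuation, which suggests that his trial ends then.
- The same section says all participants must be followed for safety until the follow-up evaluation, or longer if drug-related toxicity persists.
- Section 5.4.2 encourages dosed participants to keep attending through the two-week visit, but does not require it.

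None of these says whether the duties in criterion 2 continue after he has left.

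**3. What a dose-based period would add.** Exclusion 10 offers one length already used in this protocol: "intention to donate blood or plasma within 1 month after receiving trial drug". Taking 1 month as 28 to 31 days, the added time is:
- smallest: 28 − 14 = 14 days;
- largest: 31 − 12 = 19 days;
- nominal: 30 − 13 = 17 days.

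This is the size of the extra commitment if 1 month were chosen. It does not measure risk.

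**4. Can the documents settle whether Day 14 is long enough?** They give no half-life. Purely as an assumption, take first-order decline, with percentage remaining = 100 × 0.5^(days / half-life):

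| Assumed half-life | Remaining at 12 to 14 days | Remaining at 30 days |
|---|---|---|
| 2 days | 1.6% to 0.8% | 0.003% |
| 4 days | 12.5% to 8.8% | 0.6% |
| 7 days | 30.5% to 25.0% | 5.1% |
| 10 days | 43.5% to 37.9% | 12.5% |

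At Day 14 ±1 the result runs from under 1% to over 40%, depending on a number the protocol does not state. The documents therefore cannot decide adequacy either way.

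**The case against.** The strongest reply is that nothing here is shown to be inadequate. The length of a male precaution is a medical judgment from the Investigator's Brochure, which is not available here, and the consent form, which may tell men more, is not available either. The persistence cited in 4.2.1 followed repeated daily dosing, whereas this trial gives one dose, and detectable drug in plasma does not by itself imply a reproductive risk. Section 2.3.1 also states: "Safety data from preclinical studies with AEF0117 do not give rise to safety concerns". During the trial, condom plus spermicide and the discussion of partner contraception already protect partners. All of this stands, and it is why the point is minor.

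Three stronger readings are tempting, and the documents support none of them.
- A reader might infer from "A crossover design would have required a long washout period with a potential risk of a high dropout rate" that two weeks is too short for the male precautions. That sentence concerns carry-over in a PK comparison and gives no duration.
- A reader might take the 1-month blood donation rule as proof of inconsistency. Exclusion 10 sits with anemia, hemoglobin and recent donation of more than 250 mL, in a trial that may itself draw up to 230 mL (section 7), so blood volume is the likelier reason. It also tests intention at entry and is not a conduct rule after dosing.
- A reader might use 4.3, which ends the trial at the last participant's last visit, to claim that the period varies with recruitment. Section 4.1 gives the natural participant-level meaning, so that reading is strained.

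On reporting, it is fair to say that 7.3.10 sets no deadline for recognition, so a conception during the trial arguably falls within it whenever it is discovered. That still leaves no stated route for learning of it after the last visit.

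**Conclusion.** The point holds as a low-cost wording improvement for safety. Criterion 2 anchors the male precautions to trial time. For a completer that is 12 to 14 days after dosing, and for a dosed man who leaves early the end is not clearly fixed. Given risks that the protocol itself calls unknown and a half-life it calls long, an anchor to the dose is the better choice.

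The conclusion rests on the text of criterion 2 and the visit schedule, and needs no assumed half-life. It does not establish that Day 14 is too short, and 1 month serves only as an example length. There is no effect on the primary analysis.

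**What to change.** In criterion 2 (1.1 and 5.3.1), for male participants, replace the two references to trial time with a fixed number of days after dosing. State that it applies to every dosed man whether or not he completes. The period should run at least through Day 14 and be extended, for example to 1 month, unless the Investigator's Brochure half-life supports Day 14. The sponsor's medical lead should set the number.

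In 7.3.10, make any partner pregnancy conceived within that period reportable even if recognized after the last visit. Tell men, in the consent form and at their last contact, to notify the site.

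The cost is protocol and consent wording, with no added visit or sample. The downside is a possibly longer commitment for men: 14 to 19 days more if 1 month is chosen, and little or nothing more if the Brochure supports Day 14. Adherence cannot be checked after withdrawal of consent, because 5.4.1 then stops further data collection, but the man would still know his end date.

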#### 5.3.2 Exclusion criteria

To be eligible for participation in this trial, participants must not meet any of the following criteria at screening and/or on admission at Day -1:

1. Tobacco cigarette smokers within the last 3 months prior to dosing with trial drug.
2. Any disease or condition that might compromise the cardiovascular, hematologic, renal, hepatic, pulmonary (including chronic asthma), endocrine (e.g., diabetes), central nervous, or

gastrointestinal (including an ulcer and cholecystectomy) systems, or any clinical laboratory values assessed as potentially clinically significant by the investigator.

3. Blood pressure outside normal range (140/80 mmHg systolic/diastolic) and considered potentially clinically significant.
4. Congenital long QT syndrome.
5. A corrected QT interval (Fridericia's – QTcF) >450 msec (male) or >470 msec (female).
6. A history of alcoholism or drug addiction within the past 2 years, recent use (in the last month) of any illicit drugs, or positive results from a urine screen for substances of abuse or from an alcohol breath test.
7. A history of or current serious mental illness including active or recent suicidal ideation, severe psychological distress (e.g., active suicidal plans, psychosis, debilitating panic disorder) and/or an abnormal C-SSRS result.
8. Severe learning disability, brain damage, or pervasive developmental disorder.
9. A history of difficulty donating blood or inadequate venous access.
10. Clinically significant anemia or low hemoglobin levels (<11.5 g/dL for women and <13 g/dL for men) at screening, donation of >250 mL of blood or plasma or received any blood or plasma for medical/surgical reasons within the 30 days prior to receiving trial drug, or intention to donate blood or plasma within 1 month after receiving trial drug.
11. History of or current HIV or hepatitis B or C.
12. History of COVID-19 within 4 weeks prior to Day -1, or positive COVID-19 test, according to standard procedures at the site, at screening or Day -1.
13. Positive serum pregnancy test ( $\beta$ -hCG) at screening or positive urine pregnancy test at Day -1 confirmed by a serum pregnancy test result.
14. Allergies to the trial drug and known allergies to pregnenolone or to corn and corn derivatives.
15. Use of any prescription or over-the-counter drug therapy, including psychoactive and/or psychotropic medication, herbal, homeopathic, vitamins, minerals, and nutritional supplements, bodybuilding supplements unapproved by the sponsor, within 2 weeks prior to receiving the trial drug (for drugs with an elimination half-life greater than 10 days, this will be extended to 60 days).
16. Use of a drug therapy, or diet or supplements (e.g., St. John's Wort) food and fruit juices (e.g., grapefruit juice) known to induce or inhibit hepatic drug metabolism within 30 days prior to receiving trial drug or during the trial.
17. Legal status that would interfere with participation.
18. Unable to follow the restrictions outlined in the protocol.

---

 Screening laboratory samples must be collected between Day -28 and -2 and evaluated at the latest on Day -1. Eligibility for randomization is based on the screening results unless abnormal results from the baseline samples collected at Day -1 are available prior to randomization on Day 1.

19. Ingestion of an investigational drug or product, or participation in a drug trial within a period of 90 days prior to receiving trial drug.

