### **7.3.10 Reporting and follow up of pregnancies**

Female participants participating in this trial must be of non-childbearing potential as defined in inclusion criterion 2. Serum and urine pregnancy tests will be performed on all females regardless of childbearing potential status as specified in the schedule of activities in section 1.3.

Pregnancy is not considered an SAE but if a pregnancy occurs in a participant or in the partner of a participant during the trial, the investigator must report it to the sponsor within 24 hours using the pregnancy notification form provided by the sponsor. For females who experience pregnancy during the trial, the female participant will be monitored for any adverse problems with the pregnancy and for the outcome of the pregnancy, if feasible. This implies that a female partner to a male participant will sign a specific ICF for collection of pregnancy information.

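### The reproductive exclusions stop at a positive pregnancy test, so a breast-feeding woman who is surgically sterile is eligible as written

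*Protocol*

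**What the plan says.** Exclusion criterion 13 (protocol sections 1.1 and 5.3.2) is the only exclusion about pregnancy. It covers a positive serum test "at screening or positive urine pregnancy test at Day -1 confirmed by a serum pregnancy test result".

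Inclusion criterion 1 admits: "Healthy, non-smoking male or female of any race, 18 to 55 years old, both inclusive". Inclusion criterion 2 adds: "Heterosexually active females are only eligible if they are documented to be surgically sterile (e.g., hysterectomy, tubal ligation) or post-menopausal", together with a negative pregnancy test. Section 7.3.10 is worded more broadly: "Female participants participating in this trial must be of non-childbearing potential as defined in inclusion criterion 2". Section 5.1 sets the intended share of women: "The aim is that at least 30% of the participants will be female".

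On the drug, the pregnancy paragraph in section 2.3.1 says: "This is an experimental compound with unknown risks during conception and pregnancy in humans". Section 6.1 calls it very hydrophobic, with an estimated log P of 5.79 to 7.15. Section 4.2.1 explains that a parallel-group design was chosen because drug was still detectable 2 weeks after multiple dosing of 1 mg/day, "due to the long elimination half-life of AEF0117 in humans". Section 2.3.2 says participants should expect no immediate benefit.

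**The concern.** A negative pregnancy test shows that a woman is not pregnant. It does not show that she is not nursing, and neither does a tubal ligation. The criteria treat pregnancy as the only reproductive state that bars dosing, so a nursing infant is left out of account.

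This sits oddly with the care taken elsewhere. The protocol restricts sperm donation, requires double-barrier contraception of heterosexually active men, discusses the contraception of male participants' partners, provides for reporting of partner pregnancies, and tests every woman for pregnancy regardless of childbearing potential. Those measures already look beyond the participant to a possible child.

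What is at stake is exposure of an infant, who cannot consent, to an experimental compound in a trial that offers the mother no direct benefit. The estimate of the food effect is not at stake.

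**Working it through.** No formula applies. The check is whether any text in the protocol would stop a breast-feeding, surgically sterile woman with a negative pregnancy test from being dosed.

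**Step 1: the eligibility lists.**
- The six inclusion criteria (sections 1.1 and 5.3.1): age 18 to 55 does not exclude her. Criterion 2 accepts her through surgical sterility, with tubal ligation as a named example. None of the six mentions breast-feeding, lactation or nursing.
- The 19 exclusion criteria (sections 1.1 and 5.3.2): criterion 13 does not apply, since her tests are negative. Criterion 2 concerns disease and abnormal laboratory values, and lactation is neither. None of the 19 mentions breast-feeding.
- The dosing-day criteria (section 5.3.3): the judgment clauses concern injury to the participant's own health or a risk in her continued participation. They do not direct the investigator to consider an infant.

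**Step 2: the other places where it could appear.** The pregnancy paragraph of section 2.3.1, pregnancy reporting (7.3.10), pregnancy testing (7.4.1.3) and the screening and baseline procedures (8.1.1 and 8.1.2) are silent too. Medical history is taken at screening and updated on Day -1, but no rule attaches to an answer about breast-feeding.

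**Step 3: does the result depend on how female eligibility is read?**

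| Reading | Women admitted | Is the sterile, breast-feeding woman eligible? |
|---|---|---|
| Inclusion criterion 2, taken literally | Heterosexually active women if sterile or post-menopausal; women who are not heterosexually active are not restricted | Yes |
| Section 7.3.10 | Only women of non-childbearing potential | Yes |

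The gap exists under both readings for women sterilised by tubal ligation. Only the position of fertile women who are not heterosexually active changes between them.

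**Step 4: does the schedule contain the exposure?** Participants leave the facility after the 24-hour sample. Plasma sampling continues to 312 hours, which is 312 − 24 = 288 hours, or 12 days, after discharge. The sponsor therefore plans for drug that may be measurable well after the participant has gone home. Confinement alone does not close the gap.

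**Step 5: scale.** 0.30 × 32 = 9.6, so the minimum aim is about 10 women. This counts women, not breast-feeding women. The protocol gives nothing from which the latter number could be derived.

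**The case against.** Criterion 13 is not wrong in what it says and agrees with section 7.4.1.3, so this can be called a request for one more criterion. That is fair as far as it goes. However, eligibility is fixed in the protocol and is not normally left to a statistical analysis plan, and the present wording does admit the woman described.

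Several criteria would in practice remove many recently delivered women: any medicine, vitamin, mineral or supplement within 2 weeks (criterion 15), haemoglobin below 11.5 g/dL (criterion 10), and the requirement to be healthy. The overnight stay and seven later site visits would deter others. This lowers the likelihood but does not settle the matter, because none of these rules addresses lactation. The consent form and the investigator's brochure are not available here and may deal with it. They would not replace a criterion.

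Three stronger readings should be resisted.
- A reader might infer that all women who are not heterosexually active are eligible. Inclusion criterion 2 read alone allows this, but section 7.3.10 contradicts it, so their status is unclear.
- A reader might infer that drug will persist for 2 weeks after the dose in this trial. That observation followed multiple dosing at 1 mg/day; here each participant receives a single 1 mg dose.
- A reader might infer from the log P and half-life that a meaningful amount reaches milk. The protocol has no data on milk or infant exposure, and its statement of unknown risk is limited to conception and pregnancy.

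**Conclusion.** The point holds in a limited form and is minor. As written, the criteria admit a breast-feeding woman who is surgically sterile and has a negative pregnancy test, and no other provision in the protocol is directed at the infant. The conclusion rests on the text of the criteria and on the fact that neither sterilisation nor a negative pregnancy test excludes lactation. It does not depend on when a tubal ligation was done.

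The consequence is an unknown infant exposure, not a shown hazard. Of the roughly 10 women aimed for, few or none are likely to be affected; that is a judgment, and no specific number can be supported. Sample size, primary endpoint and primary analysis are unaffected.

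A separate inconsistency came to light in the check. Inclusion criterion 2 restricts only heterosexually active women, whereas section 7.3.10 cites that same criterion as limiting all women to non-childbearing potential. The two must be reconciled.

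**What to change.** Add breast-feeding to exclusion criterion 13 in sections 1.1 and 5.3.2, to be confirmed by asking at screening and again on Day -1, when medical history is already taken or updated. In the same amendment, reconcile inclusion criterion 2 (sections 1.1 and 5.3.1) with section 7.3.10, so that the protocol says once and consistently which women may enter.

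The cost is one phrase in two places, plus the wording needed for the reconciliation. It needs no new test or visit, and the effect on recruitment should be negligible. The change would pass through the amendment process in section 10.3.1.
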